Limitations do exist in these studies on Vitamin D level and bronchiectasis. Firstly, the studies beforehand mentioned were conducted among Caucasian and middle-east populations (26-29). It has been well reported that the aetiology of bronchiectasis varies greatly across ethnic groups (14). There is also geographical variation in epidemiology and microbiology of bronchiectasis. Secondly, relatively small sample sizes were used in these prior studies.

Our group is also conducting a prospective clinical study on serum 25-hydroxyvitamin D (25-OH D) level and risk of bronchiectasis exacerbation (UW 22-317) which started in January 2023 and targeted for completion by end of 2024. There were 104 subjects recruited who will be followed up for 12 months. In this ongoing study, 42 (39.3%) of the patients had vitamin D deficiency with baseline vitamin D level below 50 nmol/L. There were 70 patients who completed the interim analysis at 6 months. Patients who are vitamin D deficient had increased risks of developing bronchiectasis exacerbation (10% in Vitamin D deficient group and 0% in vitamin D non-deficient group), p-value = 0.082. Patients who are vitamin D deficient had increased risks of developing hospitalized bronchiectasis exacerbation (13.3% in vitamin D deficient group and 2.5% in vitamin D non-deficient group), p-value = 0.041. Patients with vitamin D deficiency also had higher SGRQ score (symptom domain) [39.4 ± 22.5 vs 28.1 ± 20.4, p = 0.011], SGRQ score (impact domain) [23.6 ± 19.3 vs 16.0 ± 14.9, p = 0.024] and total SGRQ score [29.3 ± 18.1 vs 22.9 ± 15.2, p = 0.063]. The data from this preliminary local pilot data suggested that vitamin D deficiency might have important role in bronchiectasis in terms

of symptom burden and exacerbation risks.

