The primary outcome measure is the proportion of patients who develop hospitalized bronchiectasis exacerbation during the follow-up period of 12 months, when compared with the 1-year period before. The Vitamin D deficient group will be compared with their historical data collected in the prior study entitled “Prospective clinical study on serum 25-hydroxyvitamin D (25-OH D) level and risk of bronchiectasis exacerbation” (UW 22-317) as self-control, as well as the vitamin D non-deficient group.

The secondary outcomes include the change in SGRQ, BIM and BHQ score at 6 and 12 months from baseline, as well as change in number of all/hospitalized bronchiectasis exacerbation in the follow up period of 12 months.

Those with vitamin D deficiency will be replaced with vitamin D3 at 1000 IU at the first visit. Vitamin D3 1000 IU is expected to increase blood 25-hydroxyvitamin-D level by 25 nmol/L. Blood 25-hydroxyvitamin-D level will be rechecked 3 months after replacement. If the blood 25-hydroxyvitamin-D level is still below 50 nmol/L, the vitamin D3 replacement dosage will be increased to 2000 IU. Blood 25-hydroxyvitamin-D level will be checked again at 6 and 12 months.

Patients will be followed up at 3, 6 and 12 months after recruitment. Except for the sputum analysis and blood tests, the same measures in Table 1 will be performed at 6 and 12 months. In addition, patients will be assessed on their bronchiectasis exacerbation record (both bronchiectasis exacerbation managed in an out-patient setting and hospitalized bronchiectasis exacerbation).

Methods

Blood 25-hydroxyvitamin-D level

25-hydroxyvitamin-D will be measured in nmol/L, using in-house liquid chromatography with tandem mass spectrometry (LC/MS-MS) developed by the Department of Chemical Pathology of Queen Mary Hospital. Vitamin D deficiency is defined as 25-hydroxyvitamin-D level below 50 nmol/L, while sufficient vitamin D level is defined as above 50 nmol/L, per the Endocrine Society guidelines (32, 33).

Bronchiectasis exacerbation

Bronchiectasis exacerbation was defined as [1] a deterioration in three or more of the following key symptoms for at least 48 hours, including cough, sputum volume and/or consistency, sputum purulence, dyspnea and/or exercise tolerance, fatigue and/or malaise, hemoptysis AND [2] clinician assessment that a change in bronchiectasis treatment was required usually with administration of antibiotics treatment.

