Patients will be followed up at 3, 6 and 12 months after recruitment. Except for the sputum analysis and blood tests, the same measures in Table 1 will be performed at 6 and 12 months. In addition, patients will be assessed on their bronchiectasis exacerbation record (both bronchiectasis exacerbation managed in an out-patient setting and hospitalized bronchiectasis exacerbation).

Subjects (with justification on the sample size)

Patients who participated in the prior study entitled “Prospective clinical study on serum 25-hydroxyvitamin D (25-OH D) level and risk of bronchiectasis exacerbation” (UW 22-317) will be recruited in this self-controlled study.

There were 104 subjects in the aforementioned study who will be separated into two groups according to their Baseline blood 25-hydroxyvitamin-D level: vitamin D deficient (below 50 nmol/L) and vitamin D non-deficient (at or above 50 nmol/L). There were initially 42 and 62 patients in the vitamin D deficient and vitamin D non-deficient groups respectively.

Data processing and analysis

The demographic and clinical data will be described in actual frequency or mean \pm SD, or median and interquartile range, where appropriate.

Baseline demographic and clinical data will be tabulated, as well as compared between Vitamin D deficient and vitamin D non-deficient groups by independent t-test or non-parametric tests where appropriate.

In the Vitamin D deficient group, the proportion of patients with hospitalized bronchiectasis exacerbation before and after vitamin D replacement will be compared by binary logistic regression. The number of all/hospitalized bronchiectasis exacerbation before and after vitamin D replacement will be compared by will be compared with linear regression.

The proportion of patients with all/hospitalized bronchiectasis exacerbation and between vitamin D deficient and vitamin D non-deficient groups will be compared by binary logistic regression. The number of all/hospitalized bronchiectasis exacerbation between vitamin D deficient and vitamin D non-deficient groups will be compared by will be compared with linear regression.

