Covariates including FACED score, age, gender and smoking status will be adjusted in multivariate analysis. For secondary outcome, the change in SGRQ, BIM and BHQ scores at the end of study will be compared between the two groups by linear regression and adjusted for confounders in multivariate analysis. A p-value of <0.05 will be considered statistically significant. All the statistical analyses will be performed using the latest version of Statistical Package for the Social Sciences (SPSS) software.

8. Potential hazards to subjects in the study

Patients will undergo blood tests and breathing (lung function) tests. The breathing tests may be associated with some discomfort, such as chest soreness, shortness of breath and lightheadedness. Pain, bruising or infection may occur from the needle puncture sites. Should patients' non-CF bronchiectasis significantly worsen in the course of the study, study doctor will withdraw them from the study and provide appropriate medical treatment.

Over-replacement of Vitamin D may lead to Vitamin D toxicity which can have the following symptoms: nausea, vomiting, loss of appetite, constipation, dehydration, fatigue, irritability, confusion, weakness and/or weight loss. In this study, the blood serum 25(OH)D level will be checked before the start of Vitamin D replacement and at 3 months after replacement, to ensure the replacement is adequate but not excessive.

9. Confidentiality and use of results

The demographic and clinical data collected from study subjects will be stored securely at the study site for 5 years, with access by the principal investigator or his designated research staff. These data will only be used for the study as outlined in this protocol and individual patient's identity will be removed after completion of statistical analyses.

10. Personal experience of the investigators in the field

The Division of Respiratory Medicine has a strong track record in conducting clinical research on bronchiectasis. Queen Mary Hospital is a well-recognised tertiary referral and research centre in the field of respiratory medicine, with numerous research on bronchiectasis and respiratory diseases conducted therein during the past years. All the investigators are experienced and accredited specialist. Within the last 3 years, the PI ([name]) has served as the first author of 9 out of 10 publications on bronchiectasis.

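### SGRQ, BIM and BHQ are defined as change at 6 and 12 months, but only the month-12 between-group change is analysed, leaving month 6, within-patient change in the treated group and late leavers unused

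*Protocol*

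**What the plan says.** Protocol section 7, Outcome measurement, lists among the secondary outcomes "the change in SGRQ, BIM and BHQ score at 6 and 12 months from baseline". Table 1 schedules all three questionnaires at V1, V3 and V4, that is at months 0, 6 and 12.

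Under Data processing and analysis, the only analysis given for these scores is that "the change in SGRQ, BIM and BHQ scores at the end of study will be compared between the two groups by linear regression", and this is to be "adjusted for confounders in multivariate analysis". The same paragraph says: "Covariates including FACED score, age, gender and smoking status will be adjusted in multivariate analysis". The two groups are the vitamin D deficient patients, who receive replacement, and the non-deficient patients, who do not. Their sizes are upper limits: "There were initially 42 and 62 patients in the vitamin D deficient and vitamin D non-deficient groups respectively". Deficiency is rechecked and patients must agree to join.

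Before/after comparisons within the deficient group are written for exacerbation proportions and counts only. Section 8 states that patients whose bronchiectasis significantly worsens will be withdrawn. On SGRQ, section 3 reports from the prior study, deficient versus non-deficient: "total SGRQ score [29.3 ± 18.1 vs 22.9 ± 15.2, p = 0.063", with a wider gap on the symptom domain (39.4 versus 28.1).

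**The concern.** The analysis does not cover the outcome as defined. Three things follow.

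- **Month 6.** It is a declared outcome time and the scores are collected, but no analysis of them is stated.
- **The treated group.** Only the deficient patients receive the intervention. For these scores the plan gives no estimate of how they change from their own month 0. It relies on a comparison with untreated patients who were not randomised and who, in the prior study, had better SGRQ scores.
- **Late leavers.** A patient with scores at months 0 and 6 but not 12 has no end-of-study change and contributes nothing. If such patients leave because they worsened, the remaining patients look better than the group as a whole.

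A fourth issue is how far the between-group result depends on the treatment of baseline. When groups start apart, a change-score analysis and an analysis of the follow-up score adjusted for baseline answer different questions and can disagree. The protocol gives a single analysis and does not say how sensitive the answer is to that choice.

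**Working it through.** **1. Outcome against analysis**

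| Item | Outcome and Table 1 | Stated analysis |
|---|---|---|
| Times | Months 6 and 12, from month 0 | End of study only |
| Within-patient change, treated group | Scores available at 0, 6, 12 | None for these scores |
| Patient with months 0 and 6 only | Has a month-6 change | Contributes nothing |

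**2. Are the prior-study SGRQ gaps consistent with the stated group sizes?** Inputs are the means and SDs in section 3 and n = 42 and 62, using the unequal-variance (Welch) t-test.

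- Total: gap 29.3 − 22.9 = 6.4; SE = √(18.1²/42 + 15.2²/62) = √(7.80 + 3.73) = 3.40; t = 1.89; p = 0.063, as stated.
- Symptoms: gap 39.4 − 28.1 = 11.3; SE = √(22.5²/42 + 20.4²/62) = √(12.05 + 6.71) = 4.33; t = 2.61; p = 0.011, as stated.
- Impact: gap 23.6 − 16.0 = 7.6; p = 0.026 pooled or 0.035 Welch, against 0.024 stated. This is close and fits rounding or slightly different numbers.

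The total and symptom figures fit the full 42 and 62. Both gaps exceed the 4-unit important difference given in section 7, SGRQ.

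**3. How far can two reasonable analyses differ?** Let D0 and D12 be the between-group differences at months 0 and 12, and b the slope of follow-up score on baseline score.

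- Change-score estimate: D12 − D0
- Baseline-adjusted estimate: D12 − b·D0
- Difference between them: (1 − b)·D0

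The protocol gives no slope, so b is an assumption, shown over a range.

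| SGRQ | D0 | b = 0.8 | b = 0.6 |
|---|---|---|---|
| Total | 6.4 | 0.2 × 6.4 = 1.3 | 0.4 × 6.4 = 2.6 |
| Symptoms | 11.3 | 0.2 × 11.3 = 2.3 | 0.4 × 11.3 = 4.5 |

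Against 4 units, that is 32% to 64% on total and 57% to 113% on symptoms. No BIM or BHQ gap is given, so nothing can be computed for those scores.

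**4. Loss between months 6 and 12.** In an illustrative simulation, treated patients who worsened left after month 6 and the true between-group difference was −4. The end-of-study analysis of completers gave −6.1 and a repeated-measures model using month 6 gave −4.1. Lower SGRQ is better, so the completers' result overstated the benefit. The settings are invented and the protocol gives no dropout rate, so only the direction and mechanism carry over.

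**5. What must a repeated-measures model contain?** Suppose month 0 is one of the outcomes and covariates x enter only as main effects, γ′x, the same at every visit. A patient's modelled change from month 0 to month 12 then contains γ′x − γ′x = 0, so the covariates cancel out of the change contrast. With covariate-by-visit terms the change contains (γ12 − γ0)′x, and the adjustment is kept. In simulated data with a confounder of change, the model without these terms returned the unadjusted 11.46. The adjusted change-score regression gave 6.33, and the model with the terms also gave 6.33.

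**The case against.** **A statistical analysis plan may fill the gap.** It may add detail, but here the protocol itself states an analysis, and that analysis is narrower than its own outcome. The two passages still need to be reconciled.

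**A reader might infer that the baseline score is ignored.** The documents do not support that. Baseline enters through the subtraction, and the covariate list is open-ended and followed by a general reference to confounders. The baseline score is unnamed, not excluded.

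**A reader might infer that a promised self-controlled comparison of the scores has been removed.** The protocol ties the historical self-control to the primary outcome and writes before/after analyses for exacerbations. None was promised for the scores. What stands is that a study described as self-controlled, with month-0 scores in hand, plans no within-patient estimate of them in its only treated group.

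**A reader might expect month 6 to sharpen the month-12 result.** With complete data it does not. On simulated data (42 versus 62), the change-score regression and the group-by-visit mixed model both gave 8.289, with SEs of 2.34 and 2.37. Under equal correlations, averaging the two follow-up changes would cut the variance of change by 25%, from 2(1 − r)s² to 1.5(1 − r)s². That average is a different estimand, which the protocol does not define.

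**Unequal group size might be read as a fault.** It is not; 42 versus 62 is harmless in itself.

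**The baseline gap comes from the prior study.** This is fair. Deficiency is rechecked at recruitment, the groups may change, and the total SGRQ difference had p = 0.063. The gaps indicate what to expect, not what this study will find.

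**Conclusion.** The point holds. The SGRQ, BIM and BHQ outcomes are defined and collected at two follow-up times, but the stated analysis covers one time and one contrast. Month 6 and the treated group's own change go unanalysed. Patients lost after month 6 are excluded, and the withdrawal rule makes outcome-related loss plausible. The size of any resulting bias cannot be given because the protocol states no dropout rate. The point also assumes that withdrawn patients supply no month-12 score.

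For SGRQ, the choice between change-score and baseline-adjusted analysis could move the between-group estimate by about 1.3 to 2.6 points (total) or 2.3 to 4.5 points (symptoms). This assumes slopes of 0.8 to 0.6 and prior-study gaps that persist. It measures how far two defensible analyses of non-randomised groups can disagree. It does not show that the change score is wrong.

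These are secondary outcomes of a pilot, so the weight is moderate. The change should be made because it is cheap and aligns the analysis with the outcome.

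**What to change.** For each score, replace the end-of-study regression with one linear mixed model:

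- **Outcomes:** the score at months 0, 6 and 12 as repeated measures within patient.
- **Terms:** group, visit, group-by-visit, the named covariates (FACED score, age, gender, smoking status) and covariate-by-visit. The last are essential; without them the planned confounder adjustment vanishes from the change contrasts.
- **Report:** (i) the change within the deficient group at months 6 and 12, evaluated at that group's own covariate means, and (ii) the between-group difference in change at months 6 and 12.
- **Labelled sensitivity analysis:** the follow-up score adjusted for its own baseline and the same covariates.

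If an average of the month-6 and month-12 changes is wanted, name it as an estimand.

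Two cautions belong in the text. The within-group change has no concurrent control and is descriptive. The mixed model corrects for losses only so far as the recorded scores and covariates explain them.

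**Cost:** protocol wording and a little more analysis work in the named software, with no new data or visits. The model is larger. With three visits and one parameter per covariate, covariate-by-visit adds 4 × 2 = 8 terms, which is noticeable with at most 42 and 62 patients.

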Patients who participated in the prior study entitled “Prospective clinical study on serum 25-hydroxyvitamin D (25-OH D) level and risk of bronchiectasis exacerbation” (UW 22-317) will be invited for participation during regular clinic follow-up and management in Queen Mary Hospital. If they are willing to join the further research, they will be recruited in this self-controlled study. There were 104 subjects in the aforementioned study who will be separated into two groups according to their Baseline blood 25-hydroxyvitamin-D level: vitamin D deficient (below 50 nmol/L) and vitamin D non-deficient (at or above 50 nmol/L). There were initially 42 and 62 patients in the vitamin D deficient and vitamin D non-deficient groups respectively. Patients would be rechecked for 25-hydroxyvitamin-D level to confirm the persistence of deficiency at the recruitment visit.

The following eligibility criteria will apply.

Inclusion criteria: Patients with

1. ages 18 years or above, male or female.
2. confirmed diagnosis of non-CF bronchiectasis based on high-resolution computed tomography (HRCT) scan.
3. participation in the prior study entitled “Prospective clinical study on serum 25-hydroxyvitamin D (25-OH D) level and risk of bronchiectasis exacerbation” (UW 22-317)

Exclusion criteria: Patients with

1. underlying asthma, COPD and other co-existing respiratory diseases
2. underlying osteoporosis
3. supplementary Vitamin D in their regimen
4. advanced chronic kidney disease with estimated glomerular filtration rate (eGFR) < 30mL/min

7. Brief outline of methodology

The following will be performed at the recruitment visit: Detailed medical history (Demographics, duration of bronchiectasis, co-morbidities, exacerbation history), questionnaires (SGRQ, Modified Medical Research Council (mMRC) dyspnoea scale, bronchiectasis impact measure (BIM), Bronchiectasis Health Questionnaire (BHQ)), physical examination, blood tests (Complete blood count, liver and renal function test, 25-hydroxyvitamin-D level, calcium and phosphate level, erythrocyte sedimentation rate, C-reactive protein, high-sensitivity C-reactive protein), and sputum analysis (Bacterial smear and culture, acid fast bacilli smear and culture). The detailed study procedures are summarized in Table 1. The estimated duration for each visit would be 15 minutes.

Outcome measurement

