Hospitalized bronchiectasis exacerbations are those exacerbations that fulfil the criteria above and also need at least 24 hours in-patient stay for treatment.

SGRQ

SGRQ is a disease-specific instrument designed to measure impact on overall health, daily life, and perceived well-being in patients with obstructive airway disease. Consisting of 2 parts with 50 items, it addresses frequency and severity of patients' symptoms as well as activities that cause or are limited by breathlessness. Scores range from 0 to 100, with higher scores indicating more limitations. The minimally important difference is a mean change of 4 units for slightly efficacious treatment, 8 units for moderately efficacious change and 12 units for very efficacious treatment (34, 35). SGRQ has been validated in patients with bronchiectasis and is considered a valid and sensitive instrument for determining quality of life in bronchiectasis patients (36).

BIM

Bronchiectasis Impact Measure (BIM) is another tool developed to assess patient-reported outcome in bronchiectasis. BIM is a self-administered outcome measure designed to collect patient-perceived health impact at baseline or after a follow-up period in an intervention. It was designed to address some of the perceived limitations of existing tools by being simple (eight items), giving greater scope for a range of responses (10-point visual analogue scale for each item) and by focusing on the impact of disease on quality of life rather than on the frequency or severity of symptoms. BIM consists of eight domains, namely: cough, sputum, breathlessness, tiredness, activity, general health, control, and exacerbations. A score ranges from 0 to 10 for each domain, with 10 being most severe. The total score is 80. BIM has been validated and shown to have excellent internal consistency. The domains were also shown to strongly correlate with bronchiectasis severity and exacerbation history. Statistically significant changes in all BIM domains were observed during an acute exacerbation. PI of this study translated and validated the Traditional Chinese version of BIM in year 2024.

BHQ

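### Withdrawal for significant worsening, with no provision for outcome follow-up afterwards, may leave treated-year data missing for an outcome-related reason

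*Protocol*

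**What the plan says.** The rule stands in protocol section 8 (Potential hazards to subjects in the study): should a patient's "bronchiectasis significantly worsen in the course of the study, study doctor will withdraw them from the study", with appropriate treatment then given. It applies to every participant, deficient or not. It removes the patient from the study, not only from vitamin D, and gives no criterion for significant worsening.

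Section 7 (Outcome measurement) defines the primary outcome as "the proportion of patients who develop hospitalized bronchiectasis exacerbation during the follow-up period of 12 months", compared with the year before. The comparator is historical: "The Vitamin D deficient group will be compared with their historical data collected in the prior study entitled" UW 22-317, with the non-deficient group as a second comparator. Secondary outcomes are the changes in SGRQ, BIM and BHQ at 6 and 12 months and the "change in number of all/hospitalized bronchiectasis exacerbation in the follow up period of 12 months".

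Under Methods, an exacerbation is a deterioration in at least three key symptoms for at least 48 hours, together with "clinician assessment that a change in bronchiectasis treatment was required usually with administration of antibiotics treatment". The severe form is defined so: "Hospitalized bronchiectasis exacerbations are those exacerbations that fulfil the criteria above and also need at least 24 hours in-patient stay".

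Follow-up takes place at 3, 6 and 12 months and covers the record of "both bronchiectasis exacerbation managed in an out-patient setting and hospitalized bronchiectasis exacerbation". Nothing is said about patients who have been withdrawn: collection of their outcomes is neither provided for nor forbidden.

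**The concern.** The event that ends participation and the event being counted are both a worsening of bronchiectasis that a clinician judges to need action. No threshold separates them. A patient heading for an admission is therefore more likely than others to leave the study, and the protocol does not say that an admission after leaving would be seen.

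The self-controlled design makes this one-sided. The control year was collected in an earlier study, so the section 8 rule can remove observations only from the year on vitamin D. (The withdrawal rules of UW 22-317 are not shown.) Missed admissions in the treated year would look like a benefit of replacement. With at most 42 deficient patients, a few such losses would be visible in the result.

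**Working it through.** **Where data can be lost.**
- *Admission recorded, then withdrawal.* The binary primary outcome is already met. It is lost only if the patient is later dropped or counted event-free.
- *Withdrawal for worsening, then an admission within the 12 months.* The primary event is missed unless someone looks for it.
- *Either order.* Later exacerbations may go uncounted. SGRQ, BIM and BHQ at 6 or 12 months are the most exposed, because they need the patient's continued participation.

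**Inputs.** The protocol gives no expected withdrawal rate, so there is no stated figure to reproduce and what follows is illustration.
- n = 42 deficient patients (section 6). This is an upper limit, before the recheck of deficiency and the exclusions.
- Risk of a hospitalised exacerbation p = 20% in both years, with no true effect. This is assumed, with 10% and 30% as a range. The 6-month rates in section 3 are not used: for the deficient group they print 13.3% for hospitalised exacerbations and 10% for exacerbations, although the first should be a subset of the second.
- w = share of would-be event patients withdrawn before the event is recorded; k = number of non-event patients withdrawn. Both are assumed.

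**Primary outcome, w = 25%, k = 0.** Expected events are 42 × 0.20 = 8.4; lost are 0.25 × 8.4 = 2.1; recorded are 6.3. The true odds are 0.20/0.80 = 0.25.

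Where both years of a lost patient are removed, that patient's chance of an event in the year before is p + r(1 − p), with r the between-year correlation (assumed). For r = 0.3 this is 0.44, so 2.1 × 0.44 = 0.924 earlier events leave as well. For r = 0.6 it is 0.68, so 1.428 leave.

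| Handling of withdrawn patients | Year before | Treated year | Odds ratio |
|---|---|---|---|
| All followed | 8.4/42 = 20.0% | 8.4/42 = 20.0% | 1.00 |
| Counted event-free | 8.4/42 = 20.0% | 6.3/42 = 15.0% | (0.15/0.85)/0.25 = 0.71 |
| Excluded from treated year only | 8.4/42 = 20.0% | 6.3/39.9 = 15.8% | 0.75 |
| Both years removed, r = 0.3 | 7.476/39.9 = 18.7% | 6.3/39.9 = 15.8% | 0.81 |
| Both years removed, r = 0.6 | 6.972/39.9 = 17.5% | 6.3/39.9 = 15.8% | 0.89 |

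The event-free figure hardly depends on the base risk: 0.73 at 10% and 0.68 at 30%. With w = 10% (about 0.8 patients) it is 0.88; with w = 50% (4.2 patients) it is 0.44.

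**When non-event patients are withdrawn too.** Under exclusion from the treated year, OR = (1 − w)/(1 − u), with u = k/33.6, where 33.6 = 42 × 0.80. At w = 25%, k = 4 gives 0.75/0.881 = 0.85 and k = 8 gives 0.75/0.762 = 0.98. The bias reverses above k = 0.25 × 33.6 = 8.4. With both years removed, k = 4 gives 0.89 (r = 0.3) or 0.94 (r = 0.6), and k = 8 gives 0.99 in both cases.

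**Exacerbation counts.** Suppose 4 of 42 leave at month 6 and counts are used as recorded. If they have the average rate, the treated-year total is understated by 4 × 0.5/42 = 4.8%. If they have twice the others' rate, it is understated by 4 × 2 × 0.5/(38 + 8) = 8.7%.

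**The case against.** The strongest reply is that the route to the primary outcome is narrow. The protocol counts exacerbations over 12 months, so an ordinary one is evidently not meant to end participation. If serious worsening leads to admission, that admission is the event and can be recorded before the patient leaves. Dropping withdrawn patients or coding them event-free is an analysis choice that a SAP may settle, and none is shown. Patients are "invited for participation during regular clinic follow-up and management in Queen Mary Hospital", so admissions and exacerbations could probably be found in that hospital's records. The study is also a pilot, and every rate in the illustration is assumed.

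Much of this stands, and it rules out several stronger readings:
- *That admissions are systematically removed from the primary outcome.* An admission recorded before withdrawal counts.
- *That the data are beyond recovery.* Nothing forbids later collection; only the questionnaires clearly depend on the patient's continued participation.
- *That the bias must favour vitamin D.* This holds for the before/after comparison if withdrawn patients are counted event-free. Under exclusion it depends on who else is withdrawn. Against the non-deficient group the rule acts on both sides, and the direction is undetermined.
- *That the rule would by itself produce a significant result.* With 6 patients having an event only before and 6 only after, an exact McNemar test (used here only as a gauge) reaches p = 0.031 only if all 6 later events are lost. Losing 3 gives p = 0.51.

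The objection does not remove the point itself. A SAP can choose how to treat missing observations, but it cannot supply observations that were not collected. Whether follow-up continues after withdrawal is a matter for the protocol and consent, and the protocol's only statement on the subject ends participation.

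**Conclusion.** The concern holds in a limited form. Followed as written, section 8 may leave treated-year outcomes missing for a reason related to the outcome, while the historical year is untouched by this rule. The secondary counts and questionnaire scores are more plainly exposed than the primary outcome.

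The size in this trial cannot be computed. On the assumptions used (42 patients, 20% risk, about two would-be event patients lost, no non-event patient withdrawn), a null effect would appear as an odds ratio between 0.71 and 0.89, depending on how withdrawn patients are handled. The milder end of that range belongs to the paired handling that a self-controlled design suggests. Withdrawal of non-event patients would shrink or reverse the bias under exclusion. The change is worth making because it is cheap and removes the question, not because a large bias has been shown.

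**What to change.** Reconcile the section 8 rule with the 12-month outcomes in section 7, leaving the clinical decision with the study doctor. State in the protocol, and in the consent form if it is not already there (the consent pages are not shown), that:
- withdrawal for worsening does not end outcome follow-up;
- every enrolled patient in either group who has not withdrawn consent is followed to month 12 for exacerbations and admissions through hospital records, with SGRQ, BIM and BHQ completed where the patient agrees;
- an admission that triggers withdrawal and meets the outcome definition is counted.

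The cost is a short protocol and consent amendment, plus record review to month 12 for the patients withdrawn. Their number is unknown but is likely to be small in a cohort of at most 104. Because participants attend clinic at the study hospital, the records should be within reach.
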